EXAMINATION EXTEND — HCB/2018/0906

Complete study protocol version 1.0. September 12, 2018

(NCT04462315)

Study Design

1. Title Research

Very long-term clinical outcomes of Everolimus-Eluting Stent versus Bare-Metal Stent in ST-segment Elevation Myocardial Infarction. The EXAMINATION EXTEND trial.

2. Investigator Names and sites

EXAMINATION EXTEND principal investigators

dr. [name], PhD, Hospital Clínic de Barcelona

dr. [name], PhD, Hospital Universitari de Bellvitge

dr. [name], PhD, Hospital Clínic de Barcelona

[name], MD, PhD, Hospital Clínic de Barcelona

3. Department & name head of the Department

Interventional cardiology unit, Department of cardiology, Cardiovascular institute, Hospital Clinic of Barcelona, Barcelona Spain. Institut d'Investigacions Biomèdiques August Pi i Sunyer (IDIBAPS). [name].

4. Research category

The EXAMINATION trial was originally a multicenter, randomized, controlled, superiority clinical trial to the second-generation everolimus-eluting stent (EES) with the cobalt-chromium balloon-expandable bare-metal stent (BMS) in patients undergoing

percutaneous coronary intervention (PCI) for ST-segment elevation myocardial infarction, up to 5- year follow-up. The EXAMINATION EXTEND is a retrospective, multicenter, international study to compare the 10-year follow-up clinical outcomes of primary PCI with EES versus BMS. The EXAMINATION EXTEND is an investigator-driven study with limited funding; the Spanish Heart Foundation has committed 50.000 Euro.

5. Background

Percutaneous coronary intervention (PCI) is the standard of treatment in ST-elevation myocardial infarction (STEMI) when performed in experienced Institutions within adequate time delay after the symptoms onset.¹ ST-segment elevation myocardial infarction (STEMI) represents the paradigm of a thrombotic milieu and a challenging clinical scenario to test new intracoronary devices.² In this clinical setting, first generation drug-eluting stents (DES) have demonstrated to reduce clinical and angiographic restenosis compared to BMS.³⁻⁹ Conversely, these benefits were counterbalanced by an increased risk of very late stent thrombosis.¹⁰⁻¹³ These safety concerns were confirmed by autopsy and intravascular imaging studies, showing evidence of incomplete endothelialization, delayed arterial healing, and vessel remodeling due to chronic inflammation in patients with very late stent thrombosis.¹⁴⁻¹⁹ Development of neatherosclerosis has been identified as an important player in the pathophysiology of the occurrence of very late events.

Second generation everolimus-eluting stent (EES; XienceTM V; Abbott Vascular, Santa Clara, CA) has been designed with a thin (7.8 μ m) non-adhesive, durable, biocompatible acrylic polymers and fluorinated copolymer.²⁰ As compared with first generation DES, the XienceTM V stent was able to reduce both the restenosis and the

thrombosis rates in randomised controlled trials and meta-analyses.^{21,22} The EXAMINATION (clinical Evaluation of the Xience-V stent in Acute Myocardial INfArcTION) all-comers trial was designed to compare clinical outcomes between EES and BMS in STEMI patients. At 5-year follow-up it demonstrated clinical superiority of EES over a BMS in patients with STEMI requiring primary percutaneous coronary intervention.²³

Currently available data on clinical outcome beyond 5 years are scant, especially in an important clinical scenario such as STEMI. It is therefore unknown if advantages of second-generation DES are maintained at very long-term follow-up, when incidence of neotherosclerosis is high and it may play an important role in the pathophysiology of the occurrence of very late events.

We herein sought to compare 10-year clinical outcomes of EES vs. BMS in the EXAMINATION trial, focusing on differential effects between the first 5 years and subsequent years.

6. Objectives

The EXAMINATION EXTEND study aims to examine patient and device-oriented endpoints after ten years of follow-up in STEMI patients randomly assigned to EES or BMS in the EXAMINATION trial focusing on the differences between 5 and 10 years of follow-up.

7. Methods

The EXAMINATION TRIAL is a multicentre, multinational, prospective, randomised, two-arm, single-blind, controlled trial performed in patients with STEMI (clinicaltrials.gov number: NCT00828087). It has randomized 1.498 patients to receive

either an EES (751 patients) or a BMS (747 patients). At 5 years, complete clinical follow-up was obtained in 97.3% in both arms.

A total of 12 centers in 3 countries were involved in the trial. All these centers have been contacted to prolong follow-up up to 10 years. Nine Institutions agreed to participate in this project for a total of 1.450 patients expected at 10-year follow-up.

An excel sheet was sent to all the centers to be fulfilled with 10-year follow-up of the patients included, collecting all-cause death, any myocardial infarction and any revascularization occurred between 5 and 10 years.

The primary endpoint of the study is the patient-oriented combined endpoint of all-cause death, any myocardial infarction or any revascularization at 10 year according to the Academic Research Consortium (ARC). ²⁴ The secondary endpoint of the study is the device-oriented combined endpoint of cardiac death, target vessel myocardial infarction or target lesion revascularization at 10-year. ²⁴ In addition, stent thrombosis (according to the ARC definitions²⁴) will be collected.

A clinical event committee, whose members are masked to the assigned stent, will independently adjudicate all deaths, potential myocardial infarctions, stent thrombosis, and revascularization procedures. We expect a 40% incidence of events for a total of 400 events to be adjudicated.

8. Inclusion and exclusion criteria

There are no relevant inclusion and exclusion criteria for the current extended study since this pertains to a follow-up of patients already enrolled in the main EXAMINATION trial.

9. Population

The population was the patients enrolled in the EXAMINATION trial. The study had broad inclusion and few exclusion criteria. Any patient presenting with STEMI with the following electrocardiogram criteria: at least 1 mm in two or more standard leads or at least 2 mm in two or more contiguous precordial leads or left bundle-branch block that was not known to be old, within the first 48 h after the symptoms onset requiring emergent percutaneous coronary intervention with a vessel size ranging between 2·25 mm and 4·0 mm without other anatomical restrictions could be included. Exclusion criteria were age younger than 18 years, pregnancy, patients with known intolerance to aspirin, clopidogrel, heparin, stainless steel, everolimus or contrast material, and patients on chronic treatment anti-vitamin K agents, and STEMI secondary to stent thrombosis. The patients were enrolled at 11 sites in 3 countries.

10. Endpoints

The prespecified primary endpoint of the EXAMINATION EXTEND study are the patient-oriented combined endpoint of all-cause death, any myocardial infarction, or any revascularization at 10 year according to the Academic Research Consortium (ARC) definition.²⁴ Secondary endpoints included the device-oriented combined endpoint of cardiac death, target vessel myocardial infarction (MI), or target lesion revascularization (TLR)²⁴; all-cause and cardiac death; target vessel revascularization (TVR); and, stent thrombosis (according to ARC definitions).²⁴ Detailed descriptions of the study endpoints and definitions have been reported previously.²⁵ Vital status will be verified in all patients. Independent study monitors (ADKNOMA, Barcelona, Spain) will verify the adequacy of the extended follow-up in 50% of all the patients included, together with all the reported events on-site. All events will be

adjudicated and classified by an independent event adjudication committee blinded to the treatment groups (Barcicore Lab, Barcelona, Spain).

11. Data collection

The EXAMINATION trial protocol was approved by the institutional review board of all 85 sites and is consistent with the International Conference on Harmonisation Guidance of Industry E6 Good Clinical Practice, the Declaration of Helsinki local regulations. Written consent was obtained from all participating patients when enrolled at baseline, for the duration of 5-years of follow-up.

Data collection for the entire cohort of patients will be performed via principal investigators at participating centers. Each center will be contacted by email to gather long-term results for the patients at that particular center. Teleconference calls will be performed for the site training and clarify issues.

The ethical committee will approve the protocol of the coordinating center (Ethics Committee for Drug Research, Hospital Clínic of Barcelona, Spain). After that, the study protocol approval by each site medical ethics committee approval will be requested. Once obtained, survival status and clinical outcomes will be retrospectively collected. Patient records at hospitals will be checked to assess survival status. If survival is unclear from the patient record, national death registries will be consulted to complete information on death and the specific date. In case a patient has died, the cause of death will be determined from medical records.

12. Data base information

An anonymous database of patients enrolled in the EXAMINATION trial is already available with baseline characteristics, procedural characteristics, and outcome data. All patients included in the database have been assigned a unique study number. Patient information of the patient assigned this study number is only available at individual sites. Local principal investigators will send anonymous data identifiable per unique study number to the study coordinator and principal investigator (dr. [name]). A central database will be stored at the Institut d'Investigacions Biomèdiques August Pi i Sunyer (IDIBAPS). In comparison to the already existing database, this database will be edited only by changing the duration of follow-up, date of death if this occurred, and the cause of death.

[figure not shown]
13. Statistics

A specific statistical plan analysis document will be provided. All analyses will be performed according to the intention-to-treat principle. Patients with missing follow-up data will be included in the analysis and censored at the time they are lost to follow-up or at 5-year if their recruiting hospital did not participate in the 10-year follow-up. We will analyze the primary endpoint of 10-year patient-oriented composite endpoint using Kaplan-Meier curves, with a log-rank p-value to test between-groups differences. We will use Cox proportional hazards models to estimate hazard ratios (HRs) with 95% confidence intervals (CI) comparing EES with BMS. We will do landmark analyses in the overall population, setting the landmark points at 1 and 5 years to distinguish the EXAMINATION trial results from the extended follow-up of the EXAMINATION EXTEND study. The same will be done for the device-oriented composite endpoint and the other secondary endpoints. Subgroup analyses will include the following specified

variables: gender, age >75 , presence of diabetes, post-PCI TIMI <3 , multivessel disease, ejection fraction $<30\%$, Killip class $>I$, ST-segment resolution $>70\%$, use of aspiration thrombectomy catheters, primary PCI (STEMI $<12h$), and left anterior descending as the infarct-related artery.

14. Time Schedule

EXAMINATION EXTEND Timeline

15. Administrative aspects and publication

Confidentiality and handling and storage of data and documents

Data will be stored on the Hospital Clínic local network drive with automatic overnight back-up. Stored data regarding patients and personnel included in this study can only be accessed by the investigators and the Ethics Committee for Drug Research of the Hospital Clínic (including Hospital Clínic auditors and monitors, if necessary). The processing, communication, and transfer of personal data of all participants will comply with EU Regulation 2016/679 of the European Parliament and of the Council of 27

April 2016 on the protection of individuals concerning the processing of personal data and the free movement of data, which must be complied with from 25 May 2018. If published in scientific journals or presented at scientific meetings, any information from this study will not reveal patient identity. Data will be stored for a maximum of 25 years after ending the study. Collected data will be secured against unauthorized access and stored and secured by the Hospital Clínic of Barcelona.

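### The site sheet starts at year 5 for everyone, so MI and revascularization before year 5 are never requested for the up to about 40 patients whose 5-year follow-up was incomplete (minor)

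*Protocol*

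**What the plan says.** Protocol Section 7 (Methods) describes the sheet sent to the centres as "collecting all-cause death, any myocardial infarction and any revascularization occurred between 5 and 10 years". The start point is the same for every patient. The same section states "At 5 years, complete clinical follow-up was obtained in 97.3% in both arms".

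Section 13 (Statistics) says patients with missing follow-up stay in the analysis and are "censored at the time they are lost to follow-up or at 5-year if their recruiting hospital did not participate in the 10-year follow-up".

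Section 12 (Data base information) says that, compared with the existing database, "this database will be edited only by changing the duration of follow-up", plus the date and cause of death.

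Death is handled more broadly than the other components. Section 10 has vital status checked for every patient, and Section 11 sends sites to national death registries when the hospital record is unclear. Neither is limited to the period after year 5. Section 11 also says that clinical outcomes are gathered retrospectively, but gives no start date. No section asks sites for MI or revascularization between a patient's last contact and year 5.

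**The concern.** The primary endpoint is the patient-oriented composite of death, MI or revascularization at 10 years. A 10-year time-to-first-event analysis needs unbroken observation from randomization, or censoring where observation stops. A sheet that starts at year 5 provides this for patients followed completely to year 5, but not for those lost earlier.

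Take a patient lost at year 3 whom the site can trace again. An MI or revascularization in year 4 is not requested, while anything after year 5 is. The later information cannot be joined cleanly to the earlier record, so under the stated censoring rule it is simply not used. What is at stake is a small amount of recoverable follow-up on MI and revascularization, which also feed the device-oriented composite.

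**Working it through.** **Inputs**
- Randomized: 1,498, being 751 EES and 747 BMS (Section 7). Check: 751 + 747 = 1,498.
- Complete at 5 years: 97.3% in each arm (Section 7).
- Expected incidence: 40%, with 400 events to adjudicate (Section 7: "We expect a 40% incidence of events for a total of 400 events to be adjudicated"). The two numbers do not fit the stated patient counts directly: 0.40 × 1,450 = 580 and 0.40 × 1,498 = 599, while 400 / 1,450 = 27.6%. I therefore read 40% as a 10-year incidence, as an assumption, and vary it from 30% to 50%.
- Dates of loss: not given. Assumed uniform over years 0 to 5, then varied.

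**Step 1: patients with a possible gap.** 1,498 × 0.027 = 40.4. By arm: 751 × 0.027 = 20.3 and 747 × 0.027 = 20.2.

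**Step 2: hazard.** h = −ln(1 − incidence) / 10. At 40%, h = 0.511 / 10 = 0.051 per year.

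**Step 3: first events between loss and year 5.** For loss time L uniform on 0–5, the mean probability is 1 − (1 − exp(−5h)) / (5h). At 40%: 5h = 0.255 and exp(−5h) = 0.775, giving 1 − 0.225 / 0.255 = 0.117 (unrounded inputs). Times 40.4, this is 4.8.

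**Step 4: first events between loss and year 10.** The mean probability is 1 − exp(−5h) × (1 − exp(−5h)) / (5h). At 40%: 1 − 0.775 × 0.883 = 0.316. Times 40.4, this is 12.8. This figure includes the events of Step 3.

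| 10-year incidence | First events in the gap | First events from loss to year 10 |
|---|---|---|
| 30% | 3.4 | 9.5 |
| 40% | 4.8 | 12.8 |
| 50% | 6.3 | 16.3 |

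**Step 5: sensitivity to gap length.** With a fixed gap for all 40 patients, gap events are 40 × (1 − exp(−h × gap)). For gaps of 1, 2.5 and 5 years this gives 2.0, 4.8 and 9.0 at 40% incidence, and 1.3, 3.1 and 6.0 at 27.6%. As a share of all expected events (incidence × 1,498), that is 0.3% to 1.5%. Gap and later years together come to about 7 to 16 events, or 1.7% to 2.7%.

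**Step 6: effect on power.** The protocol states no target hazard ratio. For illustration, with assumed hazard ratios of 0.75 to 0.85 and 400 or 599 events, losing 10 to 16 events lowers Schoenfeld power by less than 2 percentage points.

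**Direction of error in these figures.** All are upper bounds. They count deaths, which the vital-status check should recover. They also assume that every patient is found again, belongs to a participating centre and had no prior event.

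**The case against.** A reader might infer that the plan counts the gap as event-free, biases the 1–5 year window downward, and places patients with an unrecorded event into the event-free set at the 5-year landmark. The documents do not support that as the planned analysis. Section 13 censors at the time of loss, so a patient lost at year 3 leaves the risk set at year 3. Section 12 only lists follow-up duration among the fields that may be edited; it does not tell anyone to bridge an unobserved interval. The bias arises only if someone extends follow-up for a re-found patient despite Section 13. Neither section addresses that patient explicitly.

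A reader might also infer that the whole composite is uncollected in the gap. It is not, because deaths are covered by Sections 10 and 11.

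Further points against have weight. Censoring at first loss is a standard choice, and the rule for a patient whose follow-up resumes can properly sit in the SAP, which is not shown. Nine of 12 centres take part, the reasons for incomplete follow-up are not given, and the number of patients who could be traced again may be close to zero. The sheet itself is not reproduced; site training calls and monitoring of half the patients might bring some of this to light.

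What survives is the collection instruction. An SAP can choose a censoring rule, but it cannot supply MI and revascularization data that sites were never asked to report.

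**Conclusion.** The point holds as a minor one. For up to about 40 patients, about 20 per arm, MI and revascularization between last contact and year 5 are not requested. Under Section 13 the consequence is lost information: any 5–10 year data recovered for these patients go unused. Bias in the early window or at the 5-year landmark is conditional on follow-up being extended across the gap, which the protocol does not direct.

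The size is at most about 3–6 first events in the gap, or about 9–16 forgone from loss through year 10. This rests on uniform loss over years 0–5, a constant hazard, 30–50% 10-year incidence, all patients re-found and event-free at loss, and deaths included. Completeness was the same in both arms, so no large imbalance is implied, and the comparison of EES with BMS is unlikely to change.

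**What to change.** For participating centres, change the collection window so that it runs from each patient's date of last complete follow-up in the EXAMINATION database to 10 years, with that date pre-filled by study number. Because the sheet has already gone out, a targeted query for the affected patients achieves the same. Add to Section 7 or 13 that a patient's follow-up is extended only when the whole interval has been reviewed, and that otherwise MI and revascularization stay censored at the start of the gap.

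Cost: one date column and a sentence or two, a reissued sheet or a query for at most about 40 patients, and some checking of earlier records by sites. The gap years fall within the 5-year period that Section 11 says the original consent covered.

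### Do the expected 40% incidence and the 400 events to be adjudicated have to agree with the patient numbers in the protocol?

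*Protocol*

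**What the plan says.** The forecast is one sentence in section 7 (Methods), directly after the description of the blinded event committee: "We expect a 40% incidence of events for a total of 400 events to be adjudicated". It names no denominator, no period, no endpoint and no counting unit.

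The same section supplies the patient numbers against which a reader would check it (the point in these figures is a thousands separator). For the parent trial: "It has randomized 1.498 patients to receive" "either an EES (751 patients) or a BMS (747 patients". For its follow-up: "At 5 years, complete clinical follow-up was obtained in 97.3% in both arms". For the extension: "Nine Institutions agreed to participate in this project for a total of 1.450 patients expected at 10-year follow-up".

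Two further statements bear on what the 400 might count. The sheet sent to the centres is limited to new events, "collecting all-cause death, any myocardial infarction and any revascularization occurred between 5 and 10 years", whereas the primary endpoint is cumulative to 10 years. Section 12 (Data base information) adds that earlier outcomes are already held: "An anonymous database of patients enrolled in the EXAMINATION trial is already available with baseline characteristics, procedural characteristics, and outcome data". On checking, section 10 (Endpoints) says that independent monitors "will verify the adequacy of the extended follow-up in 50% of all the patients included, together with all the reported events on-site".

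**The concern.** The sentence reads as if 400 were the product of 40% and the cohort size. The obvious cohort is the 1,450 patients named a few lines earlier, and the product is then 580. A reader would conclude that one of the two figures is a slip, or that they rest on different bases that the text does not give.

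If so, two things would be unclear. The first is the 10-year incidence of the primary endpoint that the investigators expect. The second is how much work the event committee and the on-site monitors should prepare for, in a study that section 4 describes as having limited funding. If 40% of 1,450 is meant, the number is 580/400 = 1.45 times the one written.

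**Working it through.** **Inputs, all from section 7 of the protocol.** Incidence 40%; events 400; randomised 1,498 (751 and 747 by arm); complete 5-year follow-up 97.3%, which is 0.973 × 1,498 ≈ 1,458 patients; expected at 10 years 1,450.

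**Step 1: try to reproduce the 400 as incidence × patients.**

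- 0.40 × 1,450 = 580
- 0.40 × 1,498 = 599.2
- 0.40 × 1,458 ≈ 583
- 0.40 × 751 = 300.4 and 0.40 × 747 = 298.8

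None gives 400.

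**Step 2: work backwards.**

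- Implied base: 400 / 0.40 = 1,000. If 40% is rounded from anything between 39.5% and 40.5%, the base lies between 400 / 0.405 ≈ 988 and 400 / 0.395 ≈ 1,013. No such number is in the protocol, so rounding is not the explanation.
- Implied incidence: 400 / 1,450 = 27.6%; 400 / 1,498 = 26.7%.

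**Step 3: ask whether the two figures can both be right.** They can. Two illustrations follow, both using 1,450 and both assuming that each of the 400 is a different patient's first event, which the protocol does not say.

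- *The 40% applies only to patients still event-free at 5 years.* The base is 1,000, so 1,450 − 1,000 = 450 patients (31.0%) left it by year 5. If all 450 left because of an event, the 10-year incidence is (450 + 400) / 1,450 = 58.6%.
- *The 40% is cumulative to 10 years and the 400 are the new part.* Then 580 − 400 = 180 patients (12.4%) had an event by year 5.

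The protocol gives no 5-year event rate, so neither can be confirmed or excluded. They are not the only possibilities. The committee reviews deaths, potential infarctions, stent thromboses and revascularisations, so one patient may contribute several items and some potential infarctions may not be confirmed. A count of items for review need not equal a count of patients with a first event. Over the full 10 years, repeat events would normally push the count above 580; over years 5 to 10 alone the protocol does not fix where it would fall. The 31.0%, 12.4% and 58.6% therefore show only that compatible readings exist. They are not estimates of anything.

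**Step 4: look for anything that uses the 40% or the 400.**

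- Sample size and power: the cohort was randomised in the parent trial, and the protocol has no power statement for the extension.
- Analysis: section 13 (Statistics) specifies Kaplan-Meier curves, a log-rank test, Cox models, landmarks at 1 and 5 years, and subgroups. None takes an expected event count as input.
- Adjudication: sections 7 and 10 commit to adjudicating every event, without a cap.
- Monitoring: section 10 commits to on-site verification of every reported event, and of follow-up in half the patients. Neither is tied to 400.
- Stopping: there is no event-driven rule.

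So replacing 400 by 580, or 40% by 27.6%, would alter no procedure and no result.

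**The case for a change.** The best argument for a correction is that the protocol itself states the two figures and links them in one sentence, so this is not detail that would normally be left to the statistical analysis plan. It is the only event forecast in the document. Two readings can be made to fit, but their implied 10-year incidences, 58.6% and 40%, are 18.6 percentage points apart, so the sentence does not tell the reader what to expect. With limited funds, an adjudication load underestimated by 45% could matter in practice, and the cure is a single sentence.

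Much of this stands. The base, window and unit are missing, and 400 is not 40% of any stated patient number. What does not stand is the step from there to an error in the plan. The sentence is about items awaiting adjudication, and it sits beside a data collection restricted to years 5 to 10; a base below 1,450 is a natural reading, and on that reading 580 is not the right comparison. The sentence does not mention the primary endpoint, so it need not forecast its 10-year incidence. The 18.6-point spread comes from the first-event assumption, which the document does not support. If the workload turns out larger than forecast, the protocol still requires all of it to be done.

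**Conclusion.** No change to the plan follows. The arithmetic observation is correct: on the stated patient numbers a 40% incidence gives 580 (of 1,450) or 599 (of 1,498), and 400 corresponds to a base of 1,000 that the protocol does not mention. What this shows is an unexplained denominator in a workload forecast. It does not show a wrong figure, and the document offers no basis for saying which of the two should be altered.

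The discrepancy is 180 patients on the base of 1,450, or 199 on 1,498, if the 40% was meant for the whole cohort and the 400 counts patients with an event over the full 10 years. It may be nil if the 400 refers to new events or to a smaller base. In either case the effect on the primary comparison, its test, its hazard ratio and the completeness of adjudication is none.

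This conclusion assumes that the forecast is not used elsewhere, for example in a power statement in the statistical analysis plan, which is not at hand. Within the protocol it is not used. Anyone quoting the sentence should name the denominator, period and unit they have in mind; that is a matter of wording and not of design.

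### Section 12 limits database changes to follow-up duration and death data, which contradicts the planned collection, adjudication and analysis of non-fatal events in years 5 to 10

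*Protocol*

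**What the plan says.** Section 12 describes an existing database holding baseline, procedural and outcome data, and a central database to be kept at the coordinating institute. Comparing the two, it states that "this database will be edited only by changing the duration of follow-up, date of death if this occurred, and the cause of death".

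Other sections of the protocol plan for more than this:

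- **Section 7 (Methods).** Centres complete a spreadsheet "collecting all-cause death, any myocardial infarction and any revascularization occurred between 5 and 10 years". Stent thrombosis is to be collected as well. A masked committee "will independently adjudicate all deaths, potential myocardial infarctions, stent thrombosis, and revascularization procedures".
- **Section 10 (Endpoints).** The primary endpoint is "the patient-oriented combined endpoint of all-cause death, any myocardial infarction, or any revascularization at 10 year". The secondary endpoints include the device-oriented composite (cardiac death, target-vessel MI, target lesion revascularization [TLR]), all-cause and cardiac death, target vessel revascularization (TVR) and stent thrombosis. Monitors check follow-up in half of the patients, "together with all the reported events on-site".
- **Section 11 (Data collection).** After ethics approval, "survival status and clinical outcomes will be retrospectively collected".
- **Section 13 (Statistics).** The 10-year primary composite is analysed by Kaplan-Meier, log-rank and Cox methods. Landmark analyses follow, "setting the landmark points at 1 and 5 years to distinguish the EXAMINATION trial results from the extended follow-up". For the remaining endpoints, "The same will be done for the device-oriented composite endpoint and the other secondary endpoints".

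**The concern.** The word *only* turns the Section 12 list into a closed one. A database restricted to those three changes has no field for an MI, revascularization or stent thrombosis that a patient survived after year 5. Sections 7, 10 and 13 need exactly those fields, so both instructions cannot be carried out.

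The harm would come from the mix of what is updated and what is not. Follow-up time would be extended while MI and revascularization status stayed frozen at year 5. A patient with a first event in, say, year 7 would be carried as event-free until death or censoring, which is misclassification and not missing data. The years affected are the ones the study exists to examine: Section 6 names the difference between 5 and 10 years as its focus.

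There is a practical side too. Section 11 asks each site's ethics committee to approve this protocol before retrospective collection starts, and the original consent covered five years. A statement of which data will be changed should therefore be accurate.

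**Working it through.** No sample size, power or event figure is involved, so there is no plan figure to reproduce. The check compares what Section 12 allows to change with what each Section 10 endpoint needs after year 5.

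**Step 1: fields allowed to change (Section 12).** Follow-up duration, date of death, cause of death.

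**Step 2: fields needed after year 5 (Section 10), and whether Step 1 supplies them.**

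| Endpoint | Components | Supplied by Section 12 | Not supplied | Coverage |
|---|---|---|---|---|
| Patient-oriented composite (primary) | Death, MI, revascularization | Death | MI, revascularization | 1 of 3 |
| Device-oriented composite | Cardiac death, target-vessel MI, TLR | Cardiac death | Target-vessel MI, TLR | 1 of 3 |
| All-cause death | Death | Death | None | 1 of 1 |
| Cardiac death | Cardiac death | Cardiac death | None | 1 of 1 |
| TVR | TVR | None | TVR | 0 of 1 |
| Stent thrombosis | Stent thrombosis | None for survivors | Non-fatal stent thrombosis | 0 of 1 |

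Fully covered: 2 of 6 endpoints. Not fully covered: 6 − 2 = 4, including the primary.

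**Step 3: effect on the analyses if Section 12 is applied literally.** From year 5 onward:

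- the primary composite reduces to all-cause death, because nothing else can be recorded;
- the device-oriented composite reduces to cardiac death;
- TVR and non-fatal stent thrombosis have no new events, while the time at risk grows.

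The 5-year landmark analysis of the primary endpoint could then not be done as defined. The 10-year Kaplan-Meier estimate would count late non-fatal events as event-free time.

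**Step 4: does another part of the protocol supply the missing fields?** Section 12 names one central database. No section describes a second analysis database, or a step that merges the centres' spreadsheets or the committee's results into the central one. The outcome data already in the existing database cannot contain events from years 5 to 10 that have yet to be collected.

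**Step 5: can the number of affected events be estimated?** No. Section 7 expects 400 events for adjudication, but does not divide them by type or by period.

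**The case against.** The strongest counter-reading separates overwriting from adding. Follow-up duration, death date and cause of death are existing values that must be changed for patients already on file. Late MIs, revascularizations and stent thromboses are new records, which arrive on the spreadsheet under the study number and pass through adjudication. On that view Section 12 speaks only of the overwritten values. The reading does not survive the sentence, which compares the new database with the old one as a whole and then says *only*. It also needs a merge step that the protocol never mentions. A figure next to Section 12 is not shown in the available text, but one listing further fields would itself conflict with that sentence.

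Other objections stand in part:

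- **Not every cross-reference is equally strong.** Section 11 mentions clinical outcomes without naming a non-fatal event, and the procedures it spells out concern survival, date of death and cause of death. It is weak support. The monitoring sentence in Section 10 does not address database fields. The conflict rests on Section 7 and on the endpoints in Sections 10 and 13, which suffice.
- **The consequence is conditional.** The primary endpoint (stated in both Section 7 and Section 10), the spreadsheet, the adjudication and the on-site verification all indicate that late events are meant to be counted.
- **The counts measure textual coverage.** They say nothing about the size or direction of bias in the stent comparison.
- **The spreadsheet, as described, does not list target-vessel or target-lesion status.** This is correct. However, the Section 10 endpoints cannot be formed without it, and that section sends all events to the committee for classification as well as adjudication.

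**Conclusion.** The contradiction is real. Section 12 states a closed rule that is incompatible with the data collection in Section 7, the endpoints in Section 10 and the analyses in Section 13. It is a wrong statement in the protocol and not a detail left for the SAP, so a later SAP would not remove it.

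Read literally, the rule would leave the primary and three of the five other named endpoints incompletely recorded after year 5. The effect on the treatment comparison cannot be quantified from the document.

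The consequence rests on one assumption: that whoever builds the database follows Section 12 as written. Nothing suggests that the sponsor intends to discard events. The point should be fixed because the repair is cheap and the years at stake are the study's main interest, but it does not call the design into question.

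**What to change.** Rewrite the Section 12 sentence so that it agrees with Sections 7, 10 and 13. Besides the three items now listed, the central database should be updated with:

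- the date and adjudicated type of each MI, revascularization and stent thrombosis between years 5 and 10;
- the target-vessel and target-lesion classification of those events where the endpoint requires it;
- the classification of each death as cardiac or non-cardiac;
- the last date on which clinical status, and not only vital status, was known.

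The cost is one rewritten sentence. Design, endpoints and planned analyses stay as they are, and the events are already due for collection, on-site verification and adjudication. One practical check goes with it: confirm that the spreadsheet or the adjudication form captures target-vessel and target-lesion status, since the description in Section 7 does not mention it.
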